2.5 SGLT2i in kidney transplant recipients: Current state of knowledge

Currently, there are few published experiences on the use of SGLT2i in transplant recipients⁶³ (**Table 1**). To our knowledge, the use of SGLT2i has also been described in a few other immunosuppressed populations including heart transplant recipients. We studied 10 KTR and simultaneous pancreas-kidney transplant recipients and showed that the use of use of the SGLT2 inhibitor canagliflozin was associated with improvements in glycemic control (hemoglobin A1c (HbA1c) -0.84 \pm 1.2 %), weight (-2.14 \pm 2.8kg) and blood pressure (systolic -6.5 \pm 10.8 mmHg and diastolic -4.8 \pm 12 mmHg), which were similar in magnitude to effects reported in non-transplant cohorts. Furthermore, we did not observe any episodes of ketoacidosis, AKI, acute rejection or urinary/mycotic infections during treatment. One patient experienced hypoglycemia, and one patient developed cellulitis. Finally, there were no clinically significant changes in CNI

levels. However, this was a small cohort of patients with excellent kidney function (eGFR >60ml/min/1.73m²) where canagliflozin was initiated several years after transplantation, with a limited follow-up of 80.5 person-months. In order to better understand the efficacy, safety and potential mechanisms of SGLT2i in this unique population with variable degrees of renal impairment, further comparative studies are needed in larger cohorts of KTR.

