3.3 Anticipated Outcomes

- 1. We hypothesize that dapagliflozin will result in a significant reduction in systolic and diastolic blood pressure in a cohort of KTR with or without T2D and PTDM.
- 2. We hypothesize that dapagliflozin will be well tolerated in KTR with or without T2D and PTDM, with adverse events similar to that of non-transplant populations. We also hypothesize that there will be no clinically significant changes in CNI levels or episodes of acute rejection in KTR treated with dapagliflozin vs. placebo during the study.
- 3. We hypothesize that dapagliflozin will result in a significant natriuresis, as well as reductions in arterial stiffness, albuminuria, allograft hypoxia and markers of oxidative stress, while having neutral effects on cardiac and renal function over the course of the 12-week study period.
- 4. We hypothesize that the glucose-lowering effects of dapagliflozin will be modest in KTR with T2D or PTDM due the high prevalence of CKD in this population. In participants without T2D or PTDM, we do not expect any glucose lowering.

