4. STUDY DESIGN

This study will be a randomized, double-blind, placebo-controlled clinical trial comparing the SGLT2 inhibitor dapagliflozin to placebo in 52 KTR with or without pre-existing T2D or PTDM. The primary outcome of the trial is to determine if dapagliflozin is superior to placebo in reduction of blood pressure in KTR.

We will include incident and prevalent KTR at least 6 months after their transplant date We selected a period of at least 6 months after kidney transplantation prior to study enrolment for safety reasons. The risk of infection as well as acute rejection is highest in the early post-transplant period^{67, 68}. Furthermore, fluctuations in kidney function as well as adjustments to immunosuppressive medications are also common. Thus, a period of 6 months was selected to capture stable KTR for study inclusion.

We have selected patients with and without diabetes (including T2D and PTDM) to be included in the study for the following reasons: 1) As described in detail in the sections above, the mechanisms hypothesized to confer cardiorenal benefit are independent of improvements in glycemic control and are intact in patients with and without diabetes. Furthermore, recent large clinical trials such DAPA-HF, EMPEROR-Reduced and DAPA-CKD demonstrate that SGLT2 inhibition is safe and highly effective in non-transplant populations without diabetes, leading to approval for clinical use in multiple health jurisdictions; 2) It is still important to include KTR with T2D and PTDM as both conditions are common in the KTR population, with T2D as the cause of ESRD in approximately 30 to 40% of KTR, and PTDM occurring in approximately 25% of KTR⁴. Additionally, both conditions are associated with a high prevalence of hypertension in KTR, as well as an increased risk of cardiovascular disease, death and graft loss⁶⁹ with existing preliminary data from our centre suggesting the potential efficacy and safety of SGLT2i in a selected group of KTR with both T2D and PTDM⁶³.

In patients with diabetes, we have imposed an upper limit on HbA1c of <12.0% to avoid starting the drug in participants with poorly controlled diabetes who may be pre-disposed to ketoacidosis due to relative hypoinsulinemia. There is minimal experience with SGLT2 inhibition in patients with stage 4 or 5 CKD; therefore an eGFR of \geq 30 ml/min/1.73m² is required for inclusion. The BMI criteria is reflective of the current experience to date using SGLT2i in non-transplant populations.

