5.3 Sample Size

The sample size is based on the primary endpoint of blood pressure. Currently, there is only one publication from our group with information available on the effect of SGLT2i on blood pressure reduction in KTR with diabetes. In this observational study of 10 KTR and simultaneous pancreas-kidney transplant recipients treated with canagliflozin, we reported a SBP decrease of $6.5 \pm 10 \text{ mmHg}^{63}$. Given the small sample size in our observational study, we believe the standard deviation would be smaller in a larger cohort. Blood pressure reduction with SGLT2 inhibition appear to be similar between patients with and without diabetes in non-transplant studies. We, therefore, estimated the sample size based on a SBP change of 6.5 mmHg with a standard deviation of 8 mmHg. Under the hypothesis that SGLT2i decreases SBP by $6.5 \pm 8 \text{ mmHg}$ compared to placebo with a two-sided alpha of 0.05 and 80% power, we calculate a sample size of n=48, with 24 randomized to dapagliflozin and 24 randomized to placebo. Assuming a 10% attrition rate, the final sample size required is 52 participants. This sample size is similar to those successfully used in previous studies⁷¹, and sufficient to measure secondary renal endpoints related to renal hemodynamic function⁷¹, natriuresis and arterial stiffness⁷²⁻⁷⁴. Based on previous studies, we anticipate an even sex distribution in each group.

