9.2 Randomization, blinding and treatment allocation

The randomization scheme will be computer-generated by an independent biostatistician. To achieve a balance of participants in each arm, permuted block randomization will be used with variable blocks of 4 and 6. Randomization will be stratified based on T2D and PTDM status, as the effects of dapagliflozin may differ between these two groups. Participants will be randomized only after screening and informed consent has been obtained. All participants, nurses, physicians, study coordinators and investigators will be blinded to the treatment allocation. In addition, all participants, study personnel and study sponsor will be blinded until the end of the trial to all the laboratory and test results obtained during the trial. Dapagliflozin and placebo tablets, as well as drug packaging will be identical in appearance. Adherence to the intervention will be determined using pill counts and questioning of participants at each study visit⁸⁷. Reasons for non-adherence and drug discontinuation will be ascertained.

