# 1. Analysis for the primary objective:

- 1.1. To assess dapagliflozin-related acute and chronic changes in the primary outcome of seated systolic blood pressure compared to placebo, linear mixed-effects models will be used. Two separate models will be fit. For acute change, the vector of outcomes will include the baseline and 1-week values (i.e. Visit 3 and Visit 4 values). For chronic changes, the vector of outcomes will include the baseline and 12-week values (i.e. Visit 3 and Visit 9 values). The covariates will include the visit and treatment-by-visit interaction; due to randomization, a covariate for the main effect of treatment will not be included. The treatment-by-time coefficient, its 95% confidence interval, and its p-value will be used to assess the effect of treatment.
- 1.2. We will repeat this analysis with:
  - a. Seated diastolic blood pressure as an outcome
  - b. Seated mean arterial pressure as an outcome

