# 2. Analysis for secondary objective:

- 2.1. The numbers of hypoglycemic episodes, acute rejection episodes, volume depletion, UTI or genital infection, acute kidney injury, ketoacidosis and serious adverse events will be reported for both the placebo group and dapagliflozin group. No statistical comparisons will be performed.
- 2.2. 2.10. The same models described in the analysis of primary objective 1.1 will be completed for each of the different outcomes.

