### 4. Exploratory Subgroup Analysis.

Analyses following the forms described in 1.1 will be conducted by adding a main effect of diabetes-status and a third-level interaction term for diabetes-status by time by treatment. For 2.1, the numbers of adverse events will be calculated according to diabetes status. Analyses following the forms described in 3.2 - 3.7 will be conducted by adding a main effect of diabetes-status and an interaction term for diabetes-status by treatment.

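### Randomization is stratified on diabetes status, but the primary model and every model that reuses it omit the stratum, and the subgroup models omit diabetes-by-visit

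*SAP*

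**What the plan says.** Protocol 9.2: "Randomization will be stratified based on T2D and PTDM status, as the effects of dapagliflozin may differ between these two groups". Blocks are permuted, of size 4 and 6.

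SAP, Analysis for the primary objective, item 1.1: "The covariates will include the visit and treatment-by-visit interaction". The treatment main effect is deliberately left out, and the closing paragraph on model assumptions adds a participant-level random intercept with REML. No stratum term appears.

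This model is reused for diastolic and mean arterial pressure (1.2), for the secondary outcomes ("The same models described in the analysis of primary objective 1.1 will be completed for each of the different outcomes"), for the chemistry outcomes (3.8) and for urine adenosine (5.1). Protocol section 11 names no stratum term for the main comparison either.

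Diabetes status enters only the exploratory subgroup models of SAP section 4, by "adding a main effect of diabetes-status and a third-level interaction term for diabetes-status by time by treatment".

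The factor itself is described in more than one way. Protocol 9.2 speaks of two groups, and Protocol section 11 names T2D and PTDM as diabetes types. The SAP subgroup is diabetes versus no diabetes. Protocol section 4 also enrols people without diabetes: "We have selected patients with and without diabetes (including T2D and PTDM) to be included in the study".

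**The concern.** Stratified randomization balances the arms on the factor, so the treatment estimate varies less from trial to trial. A model that ignores the factor does not credit this. If the strata differ in mean change, the difference goes into the residual, the standard error is too large and power is lost. The estimate is not biased and type I error is not inflated.

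How much this matters depends on the outcome. For systolic pressure, Protocol 5.3 argues against a large difference: "Blood pressure reduction with SGLT2 inhibition appear to be similar between patients with and without diabetes in non-transplant studies". For HbA1c and fasting glucose, the protocol predicts a difference: "In participants without T2D or PTDM, we do not expect any glucose lowering".

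In SAP section 4 the consequence is different. With no diabetes-by-visit term, the model forces placebo change to be the same with and without diabetes. Any real difference in placebo change then has to go mainly into the three-way coefficient, which is the one tested as the treatment interaction.

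Finally, an analyst cannot code the stratum from the documents, because participants without diabetes are not clearly assigned to one.

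**Working it through.** **Inputs from the documents.** Effect 6.5 mmHg, SD of change 8 mmHg, two-sided alpha 0.05, 80% power, 24 per arm (Protocol 5.3). T2D about 30 to 40% and PTDM about 25% of kidney transplant recipients (Protocol section 4), approximated as 16 T2D, 12 PTDM and 20 without diabetes among 48. HbA1c change −0.84, SD 1.2 (Protocol 2.5).

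**Assumed, because the documents give no figure.** The between-stratum difference in mean change (D), a within-stratum baseline correlation of 0.6, and for HbA1c a baseline of 5.6% versus 7.2% and an alternative SD of 0.6.

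**The plan's own figure.** n per arm = 2(1.96 + 0.84)² × 8² / 6.5² = 23.8, so 24 per arm and 48 in total. This reproduces.

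**Formula.** For a plain comparison of change scores, with a fraction p in one stratum, the ratio of standard errors without and with the stratum is √(1 + p(1−p)D²/SD²). Here p(1−p) = (28/48)(20/48) = 0.243. For D = 2, 4, 8 the ratio is 1.008, 1.030, 1.115.

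**Planned model, systolic pressure.** Two-visit REML model with random intercept and no treatment main effect, three strata, 4,000 simulated trials. Each pair is without / with stratum and stratum-by-visit.

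| D (mmHg) | SE | SE excess | Type I error | Power at −6.5 |
|---|---|---|---|---|
| 0 | 2.044 / 2.043 | 0.0% | 4.4 / 4.6% | 87.5 / 87.4% |
| 2 | 2.057 / 2.043 | 0.7% | 4.4 / 4.6% | 87.0 / 87.4% |
| 4 | 2.096 / 2.043 | 2.6% | 4.1 / 4.6% | 86.2 / 87.4% |
| 8 | 2.245 / 2.043 | 9.9% | 2.8 / 4.6% | 83.1 / 87.4% |

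Power exceeds 80% because the model uses the baseline. With two equal strata (8,000 trials) and D = 8, power is 82.2% with no stratum term, 82.5% with a stratum main effect only and 87.1% with stratum-by-visit as well. The main effect alone therefore recovers almost nothing. A difference in pressure level only, of 5 or 10 mmHg, costs 0.3 or 1.5 power points (86.8 or 85.6 against 87.1%).

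**HbA1c.** Effect zero without diabetes, three strata, 4,000 trials. With 1:1 allocation, an effect of −0.84 confined to diabetes makes the strata differ by −0.84/2 = −0.42 in mean change.

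| Effect in diabetes, SD | Baseline gap | SE without / with | Excess | Power |
|---|---|---|---|---|
| −0.84, 1.2 | yes | 0.323 / 0.311 | 3.9% | 30.0 / 33.0% |
| −0.84, 1.2 | no | 0.315 / 0.311 | 1.3% | 32.1 / 33.0% |
| −0.3, 0.6 | yes | 0.167 / 0.154 | 8.4% | 15.9 / 18.9% |
| −0.3, 0.6 | no | 0.155 / 0.154 | 0.6% | 18.6 / 18.9% |
| −0.84, 0.6 | yes | 0.181 / 0.161 | 12.4% | 78.4 / 85.3% |
| −0.84, 0.6 | no | 0.168 / 0.161 | 4.3% | 83.3 / 85.3% |

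The −0.3 effect is the difference between the medians −0.2 and +0.1 in the randomized trial in Protocol Table 1. A separate calculation (two equal strata, SD 0.3 without diabetes and 0.6 to 1.2 with it, levels 5.6 and 7.3) gave excesses of about 4% to 18%. If placebo participants with diabetes also change by −0.5, with SD 0.6 and effect −0.4, the excess is 26% to 31%.

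**Section 4 models.** Write v for follow-up visit, t for dapagliflozin and d for diabetes, each coded 0/1. The listed terms are v, v·t, d and v·t·d. Modelled change from baseline is then:

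- placebo, with or without diabetes: β(v)
- dapagliflozin, no diabetes: β(v) + β(vt)
- dapagliflozin, diabetes: β(v) + β(vt) + β(vtd)

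So β(vtd) is the diabetes difference in change among treated participants, with no placebo difference subtracted. Simulation with 28 diabetic and 20 non-diabetic participants, true interaction zero, 4,000 trials:

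| D in placebo change (mmHg) | Mean three-way estimate | Rejection as written | Rejection with diabetes-by-visit |
|---|---|---|---|
| 0 | 0.0 | 4.7% | 5.3% |
| 2 | 1.8 | 8.4% | 5.3% |
| 4 | 3.6 | 19.1% | 5.3% |
| 8 | 7.1 | 56.0% | 5.3% |

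Adding diabetes-by-visit brings the mean estimate back to 0.1 and raises the interaction SE from 3.09 to 4.14 mmHg.

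**The case against.** **Little is at stake for the primary result.** In plausible cases the cost is about one power point. The sizeable loss needs an 8 mmHg difference, one full SD and larger than the treatment effect itself, which no document supports. This stands, and it limits the point for systolic pressure to a small gain in precision.

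**The HbA1c figures rest on chosen inputs.** This also stands as to size. With the documented effect and SD, neither model is adequately powered (30 to 33%), and the 7-point gain needs an undocumented SD of 0.6 and a baseline gap. The direction does not depend on these inputs.

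**The subgroup analysis already deals with diabetes.** It compares the groups and tests an interaction, but it does not adjust the main models, and it is the analysis that lacks a term.

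**Software with factor coding would expand the three-way term and so include diabetes-by-visit.** That coding would also restore a baseline treatment effect, which SAP 1.1 excludes. The SAP lists its terms explicitly, so it should list this one.

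**The two groups in Protocol 9.2 may mean diabetes versus none.** That reading is possible and would match the SAP subgroup. Protocol section 11, however, separates T2D from PTDM, so the text needs to settle it.

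**Adding terms to every chemistry model is excessive.** There is no evidence of stratum differences there. But the terms cost nothing material when strata do not differ, and one common model is simpler.

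**Conclusion.** The concern holds. The randomization stratum is missing from model 1.1 and from every model that reuses it. The reported standard errors are too wide whenever strata differ in mean change.

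For systolic pressure this is minor: 0.7% to 9.9% for assumed differences of 2 to 8 mmHg, with no bias, no inflation of type I error, and power above 80% at the protocol's effect and SD. For HbA1c the case is better supported, because the protocol itself expects the strata to respond differently. The main calculation gives 1% to 12%, and other assumptions give more.

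The more serious part is SAP section 4. As written, its interaction test is valid only if placebo change is the same with and without diabetes. It is an exploratory analysis, but it is applied to the primary, secondary and exploratory objectives. The between-stratum differences, the correlation and part of the HbA1c inputs are assumptions.

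**What to change.** 1. In SAP 1.1, add the randomization stratum and stratum-by-visit as fixed effects, and state that this carries through to 1.2, the secondary outcomes, 3.8 and 5.1. Code the strata exactly as in the randomization list. A stratum main effect alone is not enough.
2. In SAP section 4, add diabetes-by-visit to the models built on 1.1.
3. Reconcile Protocol 9.2 with the enrolled population and with the SAP's diabetes versus no-diabetes grouping, so that each participant, including those without diabetes, belongs to exactly one stratum.

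Cost: wording only, with no new data, visits or participants. Item 1 uses 2 degrees of freedom with two strata or 4 with three, and loses nothing material if strata do not differ (SE 2.043 against 2.044). Item 2 raises the interaction SE from about 3.1 to 4.1 mmHg, because placebo change is then estimated separately by diabetes status. The smaller figure is obtained only by assuming that the two placebo changes are equal.

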# 2. Analysis for secondary objective:

- 2.1. The numbers of hypoglycemic episodes, acute rejection episodes, volume depletion, UTI or genital infection, acute kidney injury, ketoacidosis and serious adverse events will be reported for both the placebo group and dapagliflozin group. No statistical comparisons will be performed.
- 2.2. 2.10. The same models described in the analysis of primary objective 1.1 will be completed for each of the different outcomes.

# 3. Analysis for exploratory objective:

- 3.1. ePV should be tested for equality of variances using the Welch–Satterthwaite equation.
- 3.2. 3.7. Linear regression will be performed, with treatment as a covariate. Two separate models will be fit for acute and chronic changes. Acute changes will use the baseline and 1-week values for both the dependent and independent variable values; chronic changes will use baseline and 12-week values. Exceptions include NICOM parameters will only evaluate chronic changes.

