### 3. Exploratory objectives:

- 3.1. We will determine acute and chronic effects of dapagliflozin vs. placebo from baseline on estimated plasma volume (ePV).
- 3.2. We will assess whether the proximal renal tubular natriuretic effect of dapagliflozin leads to volume contraction compared to placebo. To this end, we will determine the association between acute and chronic changes to fractional sodium handling and acute and chronic changes in volume markers.
- 3.3. We will assess whether the proximal renal tubular natriuretic effect of dapagliflozin is associated with changes in kidney function compared to placebo. To this end, we will determine the association between acute and chronic changes to fractional sodium handling and acute and chronic changes in GFR.
- 3.4. We will assess whether volume contraction with dapagliflozin leads is associated with SNS activation compared to placebo. To this end, we will determine the association between acute and chronic changes to volume markers and acute and chronic changes in markers of SNS activation.
- 3.5. We will determine whether changes in neurohormones and volume markers are associated with changes in kidney function. To this end, we will determine the

association between acute and chronic changes in absolute measures of kidney function and the acute and chronic changes in neurohormones and volume markers with dapagliflozin compared to placebo.

- 3.6. We will determine whether changes in neuro-hemodynamic & volume markers are associated with changes in arterial stiffness. To this end, we will determine the association between acute and chronic changes in arterial stiffness and the corresponding acute and chronic changes in neurohormones and volume markers with dapagliflozin compared to placebo.
- 3.7. We will determine whether changes in neurohormones and volume markers are associated with changes in blood pressure. To this end, we will determine the association between acute and chronic changes in blood pressure and the acute chronic changes in neurohormones and volume markers with dapagliflozin compared to placebo.
- 3.8. We will determine acute and chronic effects of dapagliflozin vs. placebo from baseline on urine and plasma chemistry marker levels.

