2.9. Glucose-lowering effect will be measured by HbA1c and fasting blood glucose

# 3. Outcomes for the exploratory objectives:

- 3.1. Plasma volume will be estimated [ePV] by Strauss estimation:
  - a.  $([{Hb_{baseline}/Hb_{end}} \times {(100-Ht_{end})/(100-Ht_{baseline})}]-1) \times 100$
- 3.2. Relationship between proximal renal tubular natriuretic effects and volume reduction: proximal renal tubular natriuretic effects will be evaluated by lithium clearance FE(Li+); volume change will be measured using the following outcome:
  - a. Estimated plasma volume (ePV)
    - *i.* Estimated percent change by Strauss estimation
  - $([{Hb_{baseline}/Hb_{end}} \times {(100 Ht_{end})/(100 Ht_{baseline})}] 1) \times 100$
- 3.3. Relationship between proximal renal tubular natriuretic effects and kidney function: proximal renal tubular natriuretic effects will be evaluated by lithium clearance FE(Li+); Kidney function will be measured using measured GFR.
- 3.4. Relationship between volume and SNS activation: Volume will be measured by ePV. Hormones will be measured by:
  - a. Neurohormones: Plasma aldosterone and renin
  - b. SNS markers: norepinephrine, epinephrine, dopamine, heart rate, heart rate variability (SDNN and RMSSD)
- 3.5. Relationship between neurohormones and volume markers with kidney function. Hormones will be measured by serum aldosterone and renin. Volume will be measured by ePV. Absolute measure of renal function outcomes is measured by measured GFR.
- 3.6. Relationship between arterial stiffness and neuro-hemodynamic & volume markers. Arterial stiffness outcomes will be measured by radial, aortic and carotid AIx, carotid-radial PWV and carotid-femoral PWV. Neuro-hemodynamic and volume markers will be measured by:
  - a. Seated: SBP, DBP, and MAP
  - b. NICOM: SBP, DBP, and MAP (chronic change only)
  - c. SNS: epinephrine, norepinephrine, dopamine, heart rate, heart rate variability (SDNN and RMSSD)
  - d. Neurohormones: Plasma aldosterone and renin
  - e. Volume will be measured by ePV
- 3.7. Relationship between neurohormones & volume markers and blood pressure. Hormones will be measured by plasma aldosterone and renin. Volume will be measured by ePV. Seated and NICOM (chronic change only) measures of SBP, DBP, and MAP will be the blood pressure outcomes.
- 3.8. The blood and urine biomarkers are:
  - a. Plasma chemistry:
    - *i.* Sodium, potassium, urea, phosphate, chloride, calcium
    - ii. AST, ALT, ALP, amylase

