## 4. Exploratory subgroup analyses

- 4.1. Compare diabetes vs non-diabetes status groups separately, and include test of interaction
  - a. Primary objectives
  - b. Secondary objectives
  - c. Exploratory objectives

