#### 5. Pre-specified post-hoc analyses:

- 5.1. The same models described in the analysis of primary objective 1.1 will be performed for the outcome.
- 5.2. The same models described in the analysis of exploratory objective 3.2 will be completed for each of the different outcomes.

Analysis population: The intention to treat population will be used for all analyses.

*Hypothesis testing:* For hypothesis testing, a 5% significance level will be used (two-sided). No interim analyses will be performed. For secondary objectives, nominal p-values will be reported.

*General model assumptions and model diagnostic procedures:* For the linear mixed-effects models with visit and treatment-by-visit interaction as covariates, a participant-level random intercept will be included. Restricted-maximum-likelihood will be used for estimation and the missing-at-random framework will be assumed. Plots of marginal and conditional residuals will be used for model diagnostics and assessment. Similar diagnostic procedures will be used for the linear regression models.

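### SAP analysis 3.1 prescribes a misnamed variance test for estimated plasma volume; a Welch comparison of means is the likely intent, and section 4 gives it no subgroup form

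*SAP*

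**What the plan says.** **Objective.** SAP Objectives, item 3.1: "We will determine acute and chronic effects of dapagliflozin vs. placebo from baseline on estimated plasma volume (ePV". SAP Objectives, item 1, defines acute as baseline to Visit 4 (1 week) and chronic as baseline to Visit 9 (12 weeks).

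**Outcome.** SAP Outcomes, item 3.1: "Plasma volume will be estimated [ePV] by Strauss estimation". The formula is a percent change built from hemoglobin and hematocrit at baseline and at the end visit.

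**Analysis.** SAP Statistical Analysis Plan, item 3.1, is one sentence: "ePV should be tested for equality of variances", with the Welch–Satterthwaite equation named as the means. Items 3.2 to 3.7 have their own form: "Linear regression will be performed, with treatment as a covariate".

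**General rules.** The closing paragraphs of the SAP apply the intention-to-treat population to all analyses and state that "a 5% significance level will be used (two-sided").

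**Subgroups.** SAP Outcomes, section 4, says: "Compare diabetes vs non-diabetes status groups separately, and include test of interaction", and lists the exploratory objectives under it without excepting 3.1. The matching analysis section says: "Analyses following the forms described in 3.2 - 3.7 will be conducted by adding a main effect of diabetes-status", plus an interaction with treatment. It also covers analyses of form 1.1 and the adverse event counts of 2.1. Item 3.1 is not mentioned.

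**The concern.** The analysis sentence and the objective do not match in two ways. First, the named equation does not do what the sentence asks of it. Second, even a correct test of variances would address spread, whereas the objective is about a treatment effect, that is, a difference in location. An analyst who followed the sentence literally would report no dapagliflozin effect on ePV. One who recognised the slip would have to decide what was meant, which a pre-specified plan is supposed to prevent. The subgroup section then builds on forms 1.1 and 3.2 to 3.7, so the promised interaction test for ePV has no model behind it.

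**Working it through.** The SAP states no figure for 3.1, so there is none to reproduce. The check compares the text with what the named method does.

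**1. What the equation returns.** For arms with SDs s1, s2 and sizes n1, n2:

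df = (s1²/n1 + s2²/n2)² / [ (s1²/n1)²/(n1 − 1) + (s2²/n2)²/(n2 − 1) ]

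Take n1 = n2 = 24 from Protocol 5.3, for illustration. The n terms then reduce to df = 23 × (1 + R²)² / (1 + R⁴), where R is the SD ratio:

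- R = 1: 23 × 4 / 2 = 46.0
- R = 1.5: 23 × 10.5625 / 6.0625 = 40.1
- R = 2: 23 × 25 / 17 = 33.8

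The output is a number of degrees of freedom, used to refer a difference in two means to a t distribution. It is neither a test statistic nor a p-value for equality of variances.

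**2. Whether a variance test could answer objective 3.1.** If treatment moves every value in one arm by a constant c, the difference in means changes by c, but Var(x + c) = Var(x). A variance comparison is therefore blind to the effect that the objective asks about.

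**3. Whether the contrast is specified elsewhere.**

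- Model 1.1 has a stated coefficient, 95% CI and p-value. It is assigned to 2.2 to 2.10, 3.8 and 5.1, not to 3.1.
- Model 1.1 could not simply be extended to ePV. Setting the end visit equal to baseline in the Strauss formula gives ([Hb/Hb × (100 − Ht)/(100 − Ht)] − 1) × 100 = (1 × 1 − 1) × 100 = 0. Every participant would have the value zero at Visit 3, so there is no baseline measurement to model.
- Analysis 3.2 relates FE(Li⁺) to ePV, and Outcomes 3.2 says that "volume change will be measured using the following outcome", naming ePV. If ePV change is the dependent variable there, the treatment coefficient is conditional on change in FE(Li⁺), which is measured after randomization. That is a different quantity from the overall between-arm difference in 3.1, and the SAP does not offer it as a substitute.

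**4. What is already fixed.**

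| Element | Where stated |
|---|---|
| Visits (V3–V4, V3–V9) | SAP Objectives 1; analysis 1.1 |
| Contrast (dapagliflozin vs placebo) | SAP Objectives 3.1 |
| Outcome (Strauss percent change) | SAP Outcomes 3.1 |
| Population (intention to treat) | SAP closing paragraphs |
| Level (5%, two-sided) | SAP closing paragraphs |
| Test | SAP analysis 3.1, wrong as written |

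**5. Subgroup coverage of the exploratory objectives.** Items 3.2 to 3.7 are covered by name and 3.8 through form 1.1. Item 3.1 is the only one left without a model.

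**Count.** One outcome × two periods = two contrasts with a wrong test sentence, and two interactions with no stated form.

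**The case against.** The strongest reply is that any trial statistician would read the sentence as a Welch t-test, and that such a test brings its own estimate and interval: the difference in mean percent change with its Welch CI. That is fair, and the elements fixed elsewhere support it. A second plausible reading, a variance check followed by a pooled or a Welch t-test, would change little with equal arms: the t statistic is the same and only the degrees of freedom differ. At an SD ratio of 2 the critical value moves from about 2.01 (46 df) to 2.03 (33.8 df), roughly 1%. Unequal dropout could widen this somewhat.

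It is also fair that much of the underlying information is reported anyway. Hematocrit (Outcomes 2.7.a.ii) and hemoglobin (Outcomes 3.8.a.iii) are both compared between arms by model 1.1, with the three-way diabetes-status term in section 4. The subgroup gap is an omission, since section 4 already shows the pattern to copy.

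What remains is that the sentence names the wrong procedure, and no other part of the SAP corrects it.

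**Conclusion.** The point holds as a minor error: the test sentence for one exploratory outcome is wrong as written, and section 4 omits that outcome's subgroup model. It affects two contrasts and two interactions.

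A reader might infer that the ePV effect is left wholly unspecified, or that the SAP's volume and natriuresis findings are compromised. The documents do not support either inference. Everything about the 3.1 comparison except the test is fixed elsewhere. Regressions 3.2 to 3.7 have their own form and do not depend on 3.1. The primary blood pressure analysis, the sample size and the significance level are untouched.

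That the wording and the objective disagree follows from the text and from what the equation is, and needs no assumption about the data. That a Welch t-test was intended is an inference from the equation named; the SAP does not say so, nor whether the comparison is adjusted.

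**What to change.** Replace analysis 3.1 with: *Strauss percent change in ePV from V3 to V4 and from V3 to V9 will each be compared between arms as a difference in means with 95% CI and p-value, using the Welch unequal-variance t-test with Satterthwaite degrees of freedom.*

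Add to the section 4 analysis: *For 3.1, ePV percent change will be regressed on treatment, diabetes status and their interaction, separately for each period, with heteroscedasticity-robust standard errors.* The robust errors matter because an ordinary regression would drop the unequal-variance handling that is the one thing 3.1 signals. Model 1.1 should not be used for ePV, for the reason shown above.

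The cost is two SAP sentences, with no new data and no burden on participants.
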